## STUDY PROTOCOL

### Background & Purpose of the Research

#### Primary Outcome:

1. To compare the efficacy of different non-ablative and ablative energy-based therapies for improvement in skin and skin appendages of the scalp, face, neck/décolletage, hands, upper and lower extremities, trunk and vagina.

#### Secondary Outcomes:

1. To use multi-photon microscopy (MPM) to monitor the epidermal thickening and collagen remodeling of the face after treatment with non-ablative and ablative energy-based therapies.

#### Exploratory Outcomes:

1. To compare patient satisfaction with different non-ablative and ablative energy-based therapies for rejuvenation of the scalp, face, neck/décolletage, hands, upper and lower extremities, trunk and vagina.
2. To determine the adverse event profile for different non-ablative and ablative energy-based therapies for rejuvenation of the scalp, face, neck/décolletage, hands, upper and lower extremities, trunk and vagina.

As the majority of the population ages, therapies for the improvement of skin and skin appendage disorders are becoming ever more popular for patients to ask for, and for clinicians to provide. Currently there are multiple options for skin improvement including non-invasive, minimally invasive and invasive surgery. Invasive surgeries often provide the most impressive results, however are also accompanied by a greater adverse event profile. Non-invasive therapies such as topicals (e.g. vitamin A, vitamin C, anti-oxidant serums) and chemical peels, provide nominal side effects, however results obtained using these treatments are often slight and unimpressive. Minimally invasive procedures such as fillers, botulinum toxin, radiofrequency, lasers and microneedling offer the best of both worlds with adequate results and a minimal adverse events profile with little down-time post-procedure.

The use of non-ablative (including UV lasers) and ablative devices for skin improvement is a “hot topic”. This encompasses the correction of wrinkles/rhytides, dyspigmentation, redness, skin texture (elasticity and laxity), epidermal thinning, hyper- and hypopigmentation, and skin appendage disorders. By creating minimal injury to the epidermis, these devices initiate the wound healing process, collagen remodeling and neocollagenesis, all leading to a refreshed and rejuvenated look. Advancements in technology has allowed for a boom in devices including non-ablative and ablative lasers, as well as radiofrequency. These devices have been used with efficacy for the treatment of the scalp, face, neck/décolletage, hands, trunk, and vagina in humans. In this study we would like to compare these devices in human subjects to determine which devices provide the most results with the least amount of adverse events.

We will be comparing the Fraxel Restore, Halo, Helios III, Vbeam, and Pico lasers for skin rejuvenation of the face, neck/décolletage, trunk, hands, upper and lower extremities. We will be comparing the ThermiVa and the DiVa for rejuvenation of the vagina. Lastly, we will assess the use of the PALLAS UV laser for scalp and skin appendage diseases as well as hypopigmentation disorders on the body.

To date, there are several therapeutic options for patients with signs of aging (wrinkles, uneven skin texture, laxity, dyspigmentation, redness, and follicular-based disorders) including non-invasive topicals, surgical options and minimally-invasive procedures such as energy-based devices using light, laser, radiofrequency, ultrasound, or microscopic physical damage (microneedling). Laser therapy is a safe therapeutic option for skin types I to III with little downtime and minimal side effects. New advances in technology have allowed for the development of hybrid ablative/non-ablative fractional lasers which may be safe to use in darker skin types as well. Fractionated ablative and non-ablative laser treatments have been shown to efficaciously decrease wrinkles and age spots/solar lentigines, while stimulating collagen production due to the development of microthermal treatment zones to improve on skin laxity and increase elasticity. Furthermore, non-ablative lasers, such as pulse dye lasers and targeted UV lasers can help reduce inflammation within the epidermis and dermis, thus improving redness and skin appendage or follicular-based skin disorders. Side effects of non-

ablative lasers are often minimal and reported as discomfort/pain during the procedure, erythema and edema post-procedure. Ablative lasers carry a higher risk of side effects secondary to stripping of the epidermis. Fractional technology has minimized these adverse events, however if the procedure is done incorrectly, patients and physicians have reported crusting and blistering. Radiofrequency heats the dermal collagen to induce collagen remodeling and production. With an increased dermal structure, this non-ablative technology improves skin laxity, texture, elasticity and wrinkles. Side effects of radiofrequency have also been reported as minimal with discomfort/pain during the procedure, erythema and edema post-procedure. Currently all of the non-ablative and ablative technologies to be explored in this research protocol have been well-tolerated by patients and have reports of high patient satisfaction.

Primary, secondary and exploratory outcome variables will depend on the adherence of patients to post-procedure care instructions and proper sun protection (sunscreen, protective clothing, sun avoidance) that will be provided at the end of their first visit (Visit 1, Day 1). There are no predictors to be applied to our outcomes.

This study group will consist of patients seeking improvement of either the scalp, face, neck/décolletage, hands, upper and lower extremities, trunk and/or vagina.

List up to ten relevant references/articles to support the rationale for the research:

1. Gold, MH. The future of non-invasive rejuvenation technology: devices. *JDD*, 16(6):s104-7, 2017.
4. Peet, JJ. Evaluation of the safety and efficacy of hybrid fractional 2940 nm and 1470 nm lasers for treatment of vaginal tissue: pilot study. 2600-003-15 Rev. A, Sciton, Inc.
5. Pozner, J, Robb, C. Hybrid fractional laser: the future of laser resurfacing. 2600-003-13 Rev A, Sciton, Inc.

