## Research Procedures

We expect that screening patients for inclusion in this study will take two to three months total. Subjects will be screened for participation from the patient population of the UC Irvine, Department of Dermatology. Once a subject is chosen as a possible candidate, the research study team will discuss with the patient whether they would like to participate in a research study comparing non-ablative and ablative energy devices for skin improvement. It will be made clear to patients that modalities such as Fraxel, Halo, Helios, Vbeam, and Pico have been found to be efficacious for improvement of the skin of the face or body while ThermiVa and DiVa have been found to be efficacious for rejuvenation of the vagina, and PALLAS for the scalp or hypopigmentation disorders. Patients will be told that photographs of their scalp, face, neck/décolletage, trunk, hands, upper and lower extremities, and /or vagina depending on the treatment site will be taken and will possibly be used for publications and presentations in the future; it will be made clear to patients that all efforts will be taken to de-identify the photographs. Risks will be explained thoroughly to patients. If patients decide that they would like to participate, they will be given a copy of the informed consent either to take home and read for up to 2 weeks, or if they feel comfortable reading in a private room to read for a maximum of 2 hours before obtaining a signature. Once patients consent to participation, they will be scheduled for their first visit, which may be as early as on the same day as their screening visit.

If eligible, patients may opt to have multiple sites treated during the study.

At their first visit (Visit 1, Day 1), patients' inclusion/exclusion criteria will be reviewed, demographic information will be obtained, physician-assessment performed, vitals assessed, and photographs (before and after treatment) will be taken. Patients will then receive the energy-based treatment in one or more areas. Information regarding the area treated, the device used and the machine settings will be recorded in detail. Patients will be given a diary to fill out to assess for side effects and the timeline of resolution.

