## **Study Design**

This study will be designed as a prospective clinical trial to compare various energy-based devices for the improvement of the scalp, face, neck/décolletage, trunk, hands, upper and lower extremities, and vagina. If patients meet the inclusion and exclusion criteria for multiple treatment areas, they will be allowed to receive treatment for multiple areas. The treating physician will decide which energy-based device is best-suited to address the patients' aging concerns; although patient preference will be taken into account, ultimately the treating physician is responsible for the correct assessment of the patients' needs, the use of the appropriate energy-based devices, and the final treatment. Although this may lead to some bias, patients will be treated in the most appropriate manner for their disease. Patients will be followed for 3 months post-treatment to determine if the procedure was efficacious for rejuvenation of the treatment anatomical area.

Per statistical considerations outlined below we will be comparing non-ablative and ablative devices. For each body area studied, 10 patients will be enrolled each into the non-ablative and the ablative device groups. The decision to treat and which device will be used will be made by the physician after careful consideration of a subject's rejuvenation concern(s). Multiple devices may be used due on one subject; for instance, a subject may require facial, body and/or vaginal rejuvenation, in which case one of the devices such as the Fraxel, Halo, Helios, Vbeam, or PicoWay would be used to address the face or body with the device picked based on the subject's needs or concerns, while either the ThermiVa or the DiVa would be used for vaginal rejuvenation, and PALLAS would be used for the scalp or hypopigmentation concerns.

A retrospective electronic medical record review will also be completed as part of this study to capture patients who were previously treated with any of the aforementioned modalities for rejuvenation of either the face, neck/décolletage, hands, trunk, upper and lower extremities and/or vagina.

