The study endpoint will be 3 months. Number of laser treatments needed during this time period will be based on the patient's clinical response to each treatment (as assessed by the physician). Evaluation will occur using various validated methods including photographs, MPM imaging, the Global Aesthetic Improvement Scale, the Visual Analogue Scale, the Modified Fitzpatrick Wrinkle Scale, the Wrinkle Severity Rating Scale, the Facial Laxity Improvement Scale, the Dyspigmentation Scale, the Mid-Clavicular Nipple Distance, the Fabi Bolton Chest Wrinkle Scale, the Merz Hand Grading Scale, the Vulvo-vaginal Laxity Questionnaire, Female Sexual Function Index, International Consultation on Incontinence Questionnaire – Short Form, Severity of Alopecia Tool, Psoriasis Scalp Severity Index, Patient Global Impression of Change, and Clinician Global Impression (based on which body site and laser are used).

There are no composite variables as the primary outcomes will only be determined by the physician and subject GAISSs. Other criteria for evaluation (secondary and exploratory outcomes) include photographs, the Modified Fitzpatrick Wrinkle Scale, the Wrinkle Severity Rating Scale, the Facial Laxity Improvement Scale, the dyspigmentation scale, the mid-clavicular nipple distance, the Fabi Bolton Chest Wrinkle Scale, the Merz Hand

Grading Scale, the Visual Analogue Scale for pain, the patient diary, and the investigator-authored patient satisfaction survey.

At each study visit, the investigator/physician will collect physician and subject-reported data regarding the efficacy and adverse events associated with the procedure (Visits 2-5, Days 14-90). To define patient satisfaction, an investigator-authored survey will be completed at the last visit (Visit 5, Day 90). Photographs will be collected at all visits (Visits 1-5, Days 1-90).

Since use of the PALLAS laser is typically required twice weekly, treatment of scalp and hypopigmentation disorders will follow a separate schedule of events from the other energy-based devices. Subject will receive 24 treatments over 12 weeks (Visits 1-24), with patient and clinician assessments and clinical photos taken at every other visit (Visit 2, 4, 6, 8, 10, 12, 14, 16, 18, 20, 22, 24). A blinded clinician will also assess change in skin or hair at Visit 12 and 24. Visit 25 will consist of a one-month follow up after the three-month treatment period.

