## **STATISTICAL ANALYSIS PLAN**

Statistical analysis of the data will be limited given the small sample size. Given the scales used for evaluation, data will be recorded as continuous scores. Statistical analysis will be completed using non-parametric methods (with significant defined as  $p < 0.05$ ) due to the subjective nature of the quantitative scales of improvement used and possible skew of results. Given that multiple areas will be treated and monitored for improvement over time, we may need to apply the Bonferroni Correction. If and when dependent samples are reported (i.e. longitudinal measures on individual patients), analysis will be completed with either the Mann-Whitney-Wilcoxon Test (two observations) or Friedman's test (more than two observations). When possible, trend evaluated over time will be assessed using a non-parametric test for trends over ordered groups. Bonferroni correction will be used to account for multiple comparisons. Analysis will be completed using STATA, version 13.

Power and sample size will be determined based on primary outcome- to compare the improvement between ablative and non-ablative therapy in face, décolletage, hands, trunk, upper and lower extremities, and vagina. Given the 7 regions to compare, Bonferroni correction was used to define the new significance level as  $0.05/7=0.007$ . Sample sizes of 10 in ablative and 10 in non-ablative group in each body region achieve 81% power to show a difference in means when there is a difference of 2.0 between the null hypothesis mean difference and the actual mean at the 0.007 significance level (alpha) using a two-sided Mann-Whitney-Wilcoxon Test.

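### Any ablative versus non-ablative comparison on the secondary and exploratory severity scales would carry over baseline differences, because device class is chosen by the physician and no baseline adjustment is planned

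*Combined protocol and SAP*

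**What the plan says.** - **Predictors.** Background & Purpose of the Research, at the end of the text under Exploratory Outcomes: "There are no predictors to be applied to our outcomes". The sentence before it concerns primary, secondary and exploratory outcome variables alike.
- **Allocation.** Study Design: "The treating physician will decide which energy-based device is best-suited". The same paragraph concedes "Although this may lead to some bias" and gives no analytic remedy.
- **Visit 1.** Research Procedures lists, for the first visit, "demographic information will be obtained, physician-assessment performed, vitals assessed, and photographs (before and after treatment) will be taken". It continues: "Patients will then receive the energy-based treatment in one or more areas". The assessment therefore comes before treatment, but no scale is named.
- **Outcomes.** Study Design says that "the primary outcomes will only be determined by the physician and subject GAISSs". The severity scales come lower: "Other criteria for evaluation (secondary and exploratory outcomes) include photographs, the Modified Fitzpatrick Wrinkle Scale, the Wrinkle Severity Rating Scale", followed by the dyspigmentation, chest and hand scales among others.
- **Analysis.** The SAP gives the Mann-Whitney-Wilcoxon test, Friedman's test, a non-parametric trend test and a Bonferroni correction. For the comparison of device classes it names no covariate, stratification, matching or change-from-baseline definition. The power statement reads "Sample sizes of 10 in ablative and 10 in non-ablative group in each body region".

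**The concern.** The score on a severity scale before treatment is usually a strong predictor of the later score on that scale. Without randomisation, nothing makes the two classes start level. If one class is given to more severely affected skin, an unadjusted comparison mixes that starting difference with the effect of the device. Even with equal starts, ignoring the earlier score usually wastes precision, which is scarce with 10 patients per class and region.

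At stake is how any class difference on the wrinkle, chest, hand and dyspigmentation scales can be read. The direction of the error depends on a choice that the SAP leaves open, namely whether raw follow-up scores or changes from baseline are compared.

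**Working it through.** **Inputs from the documents.** 10 v 10 per region; two-sided Mann-Whitney-Wilcoxon test; nominal level 0.05, or 0.05/7 = 0.00714, rounded to 0.007; no covariate.

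**Assumptions (not in the documents).** Correlation ρ between baseline and follow-up score of 0.3, 0.5 or 0.7; equal SDs; a linear relation; normal scores; higher score means worse; a baseline gap D of 0, 0.5 or 1 SD.

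**1. The plan's own figure.** The SAP states 81% power for a difference of 2.0 at 0.007 but gives no SD, so the figure can only be solved backwards. Under the normal approximation, power = Φ(δ/(σ√(2/n)) − z). With σ = 1.25: 2/(1.25 × √0.2) = 3.58; 3.58 − 2.70 = 0.88; Φ(0.88) = 81%. A t test needs σ of about 1.12, and a t test with the Wilcoxon efficiency 3/π about 1.09. Simulating the exact rank-sum test gives 80.4% at σ = 1.10. This figure belongs to the primary comparison, so it is not evidence for or against the present point.

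**2. Precision with equal baselines.** The variance of the adjusted comparison relative to unadjusted follow-up scores is (1 − ρ²)(1 + 1/16), where the second factor is the cost of one covariate at 10 v 10.
- ρ = 0.3: 0.91 × 1.0625 = 0.97
- ρ = 0.5: 0.75 × 1.0625 = 0.80
- ρ = 0.7: 0.51 × 1.0625 = 0.54

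Break-even is at ρ² = 1 − 1/1.0625 = 0.059, so ρ is about 0.24. Below that nothing is gained.

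**3. Carry-over of a baseline gap D when there is no effect.** Raw follow-up scores differ by ρD; change scores differ by −(1 − ρ)D. For D = 1 SD:

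| ρ | raw | change | adjusted |
|---|---|---|---|
| 0.3 | +0.3 SD | −0.7 SD | about 0 |
| 0.5 | +0.5 SD | −0.5 SD | about 0 |
| 0.7 | +0.7 SD | −0.3 SD | about 0 |

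The signs are opposite, so using change scores does not cure the problem.

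**4. Simulation, 10 v 10.** Rank-sum test on raw or change scores, against a regression of ranked follow-up score on class and ranked baseline score. Separate runs of 4,000 to 40,000 data sets per setting agree to within about one percentage point. Results are for ρ = 0.3/0.5/0.7.

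| Setting | level | raw | change | adjusted |
|---|---|---|---|---|
| True effect 1 SD, equal baselines (power) | 0.05 | 51/51/51% | not needed here | 56/62/76% |
| No effect, D = 1 SD (false positives) | 0.05 | 8/16/28% | 21–22/16/11–12% | 5–7% |
| No effect, D = 1 SD (false positives) | 0.007 | 1.7/4.3/9.0% | 6.2/4.3/2.7% | about 1% |

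With no effect and no gap, the rank-sum test rejects in 4 to 5% and rank ANCOVA in about 5%, so only a small part of the power gain comes from the rank-sum test being conservative.

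With a true benefit of 1 SD, the treated class starting 0.5 SD worse and ρ = 0.5, rejection at 0.05 is about 32% on raw scores, 70% on change scores and 58% adjusted. Raw scores tend to hide the benefit, and change scores exaggerate it.

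**5. Where the gain is bias removal only.** With D = 1 SD and ρ = 0.5, the adjusted variance relative to unadjusted is 0.75 × (0.2 + 1.2/16)/0.2 = 1.03. Here 0.2 = 2/n, and 1.2 = D² + 2/n is the expected squared observed gap. At that imbalance adjustment adds no precision; it removes the bias.

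**The case against.** **The criticised comparison is not spelled out.** The SAP's one explicit class comparison is for the primary outcome. The stated secondary objective is microscopy, and the exploratory objectives are satisfaction and adverse events. The severity scales are only further criteria for evaluation, and the SAP's longitudinal tests work within patients. This stands, so the point is conditional: it applies to any class comparison made on these scales. Comparing therapies is nevertheless the stated aim, and the plan offers nothing else for doing so on these scales.

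**A reader might infer that the primary analysis is compromised.** The documents do not support that. The primary outcome is an improvement rating by physician and subject, with no baseline value to carry over.

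**A reader might infer that the plan prescribes an unadjusted Day 90 comparison, which would hide a benefit or show a false harm.** That is not stated either. The SAP speaks of improvement and does not choose between raw and change scores. With change scores the error runs the other way.

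**A reader might assume that the baseline scores are certainly available.** Research Procedures names no scale at Visit 1, and Study Design ties efficacy data to Visits 2 to 5. For the UV laser, scheduled assessments fall on even visits. The schedule tables are not in the text reviewed. Scoring before treatment is a reasonable inference, not a documented fact. Nor do the documents say who scores these scales.

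**The sentence on predictors may mean little.** It sits in the background text after a remark on adherence to aftercare and sun protection, and may say only that no predictors are under study. This is fair; the SAP's silence on covariates is the firmer ground.

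**The size is assumed.** No document supports a gap of 0.5 or 1 SD; devices are assigned by concern and need, and severity is not mentioned. At ρ = 0.3 the gain is modest, and at 0.007 the absolute false-positive rates are much lower than at 0.05.

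**Conclusion.** The concern holds for the secondary and exploratory severity scales only. With device class chosen by the physician and no baseline adjustment planned, a class comparison on these scales passes on a share of any starting difference: ρ of it on raw scores, and 1 − ρ of it in the opposite direction on change scores.

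For an assumed ρ of 0.3 to 0.7, the power lost at 0.05 with equal baselines is about 5 to 25 percentage points (51% v 56%, up to 51% v 76%). With a 1 SD gap and no effect, false positives on raw scores are roughly 1.6 to 5.6 times the nominal 5% (8% to 28%); at 0.007 they are about 2 to 9%. These figures rest on assumed correlations, gaps and normal scores, and show scale rather than forecast this trial.

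Leaving raw versus change open adds a further problem, since the two are biased in opposite directions and the choice could be made after the data are seen. Adjustment for baseline severity would not remove confounding by the type of concern or other reasons for choosing a device.

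**What to change.** Replace the background sentence on predictors and add to the SAP:

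> For each severity scale scored before treatment at Visit 1, the score at that schedule's final efficacy visit is compared between device classes by rank ANCOVA with the Visit 1 score on that scale as covariate. Classes are not compared through separate within-class p-values. Confounding by the reason for device choice remains and is reported as a limitation.

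Three details are needed with it:

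- State which scales are scored at the Visit 1 physician assessment, and that this is done before treatment.
- Name the final efficacy visit separately for each schedule. Day 90 does not serve for all: micro-coring has follow-up at Day 90 and Day 150, and the UV laser schedule runs by numbered visits to Visit 25.
- Say that the primary improvement rating is analysed without this covariate because it has no baseline value.

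**Cost.** If the scales are already scored at Visit 1, this is a change of analysis wording and one degree of freedom. If they are not, the scores must be added to the Visit 1 data collection. The precision gain is small if ρ is low, and absent below about 0.24.
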